18 FEB 2023										
RESEARCH & ETHICS COMMITTEE [name]										
i.	AIDS is a disease which has no cure									
ii.	Reduces the body's natural defense against illness									
iii.	Everyone with HIV has AIDS									
iv.	Bodies show signs of AIDS in a shorter time									
v.	Progression of HIV to AIDS can be slowed									

by getting into care and living positively

vi. Someone on ARVs who does not take ARV well will develop resistant virus

		
--------------------------	--------------------------	--------------------------

8. HIV Discordance is when a partner in a stable relationship tests HIV positive while the other tests HIV negative. Discordance is common. The following is true about discordance:

Agree (1) Disagree (2) Don't Know (3)

i. Discordance is a sure sign that someone has been unfaithful.

		
--------------------------	--------------------------	--------------------------

ii. A couple can remain discordant for a very long time

		
--------------------------	--------------------------	--------------------------

iii. The negative partner is always at risk.

		
--------------------------	--------------------------	--------------------------

iv. Couples can reduce risk by using condoms correctly and consistently during sex

		
--------------------------	--------------------------	--------------------------

v. HIV positive partner should start ARV's as soon as possible

		
--------------------------	--------------------------	--------------------------

9. The following is true about ART

Agree (1) Disagree (2) Don't Know (3)

i. When one is tested for HIV and started on ARVs that first treatment is called first line.

		
--------------------------	--------------------------	--------------------------

ii. Your clinician may decide to change your drugs to a new type called second line

		
--------------------------	--------------------------	--------------------------

because the first line drugs have stopped working.

iii. First line stops working if you don't adhere well

		
--------------------------	--------------------------	--------------------------

iv. First line stops working if you get a resistant virus or have been on the drugs for a very long time

[figure not shown]
		
--------------------------	--------------------------	--------------------------

v. Main cause of first line failure is poor/ inconsistency drug swallowing and many other reasons.

		
--------------------------	--------------------------	--------------------------

Study Staff Name	Signature	Date ____/____/____
---------------------	-----------	------------------------

CFL Youth Study Knowledge Questionnaire, adapted from CFL RCT

CFL YOUTH STUDY

x. SEXUAL BEHAVIOR QUESTIONNAIRE

Section A: Patient Information

1. Patient clinic #

--	--	--	--	--

2. Study Number

--	--	--	--	--

3. Visit code: • 4. Visit date / /
DD/MM/YYYY

Section B: Attitudes and sexual practices

5. Do you currently have a regular/ steady partner?

 Yes No (skip to 7)

[figure not shown]
6. If yes to Qn 5 above, how long have you been with this partner?

 Years Months

7. Have you ever had a partner =/ >10 years older than you?

 Yes No

8. At what age was your sex debut?

 Years (N/A)

9. After knowing your HIV Status, has your attitude towards having sex changed?

 Yes No

10. If yes to Qn 9 above, which of the following best describes your change in sexual practices?

 Abstinence Use of condoms Reduced number of sexual partners Reduced number of sexual encounters I lost interest in sex

[figure not shown]
- Increased number of sexual partners
- Increased number of sexual encounters

11. HIV positive persons should abstain from having sexual intercourse?

- Agree
- Disagree
- Do not know

12. When was the last time you had sexual intercourse?

- Hours ago
- Days ago
- Weeks ago
- Months ago
- Years ago
- Never

13. If months or years ago, what is the most common reasons which prevented you from having sexual intercourse?

- No partner
- My health status
- Health status of my partner
- Am abstaining
- Other (specify)-----

14. The last time you had intercourse did you use a condom?

- Yes
- No
- Do not remember

15. The last time you had intercourse had you been drinking alcohol or marijuana in the few hours before?

- Yes
- No
- Do not Know

16. How many times in the last 2 months have you had sex without a condom?

- None

1-3
 3-10
 >10

17. Do you regularly use condoms?

Yes
 No

18. In the last 3 months, have you had any abnormal discharge/ ulcer/wound in your genito-urinary part?

Yes No (skip to 20)

19. If Yes, did you receive treatment

Yes, went to health worker
 Yes, I self-medicated
 No, I did not

20. Have you ever had forced or coerced sex?

[figure not shown]
Yes
 No (if no end here)

21. If yes to Qn 20 above, did you inform any one?

Yes
 No

22. If yes to Qn 21 above, whom did you inform?

Police
 Friend
 Relative (Specify relationship eg, Mum, sister, aunt)

Study Staff Name / Initials	Signature	Date
  		____ / ____ / ____ DD/MM/YYYY

xi. COVID-19 KNOWLEDGE ASSESSMENT AMONG YOUTH (BASELINE ONLY)

Section A: Patient Information							
1. Clinic number#	2. STUDY Number :			3. Date of Visit _____ / _____ / _____			
Have you ever heard or know about Corona Virus disease 2019? Yes  No  (if no stop)	Family/ friends 	Radio 	Newspaper 	Social media 	Internet 	Religious leader 	Medical personnel 
Where do you get your knowledge about Coronavirus?							

Questions developed using information from WHO <https://www.who.int/news-room/q-a-detail/q-a-coronaviruses>

Section B. Do you know any Symptoms of COVID-19								
Symptoms	Yes	No	Days	Symptoms	Yes	No	Days	
Fever				Aches and pains				
Dry cough				Nasal congestion/runny nose				
Sneezing				Sore throat				
Loss of smell				Loss of taste				
Shortness of breath				Diarrhea				
Have you had any symptoms above? List symptoms and action taken								

Section C. Knowledge about PROTECTION				Section D. Practices about PROTECTION (last 7 days)			
		Agree	Disagree	Don't know	Yes	No	NA
Regularly and thoroughly clean your hands with an alcohol-based hand rub							
Regularly and thoroughly wash your hands with soap and water.							
Maintain at least 1 metre (3 feet) distance between yourself and anyone who is coughing or sneezing.							
Avoid touching eyes, nose and mouth							

[figure not shown]
[figure not shown]
MAKERERE UNIVERSITY
SCHOOL OF MEDICINE
RENEWAL
VALID UNTIL

★ 10 FEB 2023 ★
RESEARCH & ETHICS COMMITTEE
[name]
Page 100 of 103

Covering your mouth and nose with your bent elbow when you cough or sneeze.						
Covering your mouth and nose with tissue when you cough or sneeze. Then dispose of the used tissue immediately						
Stay home if you feel unwell						
Keep up to date on the latest COVID-19 hotspots						
Wear a mask if you are ill with COVID-19 symptoms (especially coughing)						
Wear a mask if you are looking after someone who has COVID-19 symptoms						
Disposable face mask that can only be used once						

Section D. Other knowledge

	Knowled geable	Partially	Not knowledge able
What would you do if you have symptoms of Coronavirus? Answer 1) Self quarantine 2) Wear a mask 3) Call help line number			
Do you have with you any help line number? Which one would you call if you or anyone near you has COVI-D symptoms?			
Should you put a mask to protect yourself? Answer: Only wear a mask if you are ill with COVID-19 symptoms (especially coughing) or looking after someone who may have COVID-19.			
Do you know how to use a mask? Answer. 1) Before touching the mask, clean hands with an alcohol-based hand rub or soap and water 2) Place the mask to your face. 3) Pull down the mask's bottom so it covers your mouth and your chin. 4) After use, take off the mask and Discard the mask in a closed bin immediately after use 5) Perform hand hygiene after touching or discarding the mask – Use alcohol-based hand rub or, if visibly soiled, wash your hands with soap and water			

Questions developed using information from WHO

<https://www.who.int/emergencies/diseases/novel-coronavirus-2019/advice-for-public/myth-busters>

Section E. Knowledge about MYTHS				Section D. Practices about MYTHS (last 7 days)		
	Agree	Disagree	Don't know	Yes	No	Not sure
Exposing yourself to the sun or to temperatures higher than 25C degrees prevents the coronavirus disease (COVID-19)						
Being able to hold your breath for 10 seconds or more without coughing or feeling discomfort means you are free from the coronavirus disease (COVID-19) or any other lung disease.						
Drinking alcohol protects you against COVID-19 and can be dangerous						
COVID-19 virus cannot be transmitted in areas with hot and humid climates						
Taking a hot bath prevents the new coronavirus disease						
The new coronavirus is transmitted through mosquito bites.						
Hand dryers effectively kill the new coronavirus?						
Spraying alcohol or chlorine all over your body kills the new coronavirus						
Eating garlic prevents infection with the new coronavirus						
The new coronavirus affects older people, and younger people are not susceptible						
Antibiotics are effective in preventing and treating the new coronavirus						
Chloroquine is effective in preventing and treating the new coronavirus						

Section F. HIV care

[figure not shown]
ART medications

Do you have antiretroviral drugs with you at the moment? Yes No

Are you taking your ART?

Yes No

Rate your adherence in the last month _____

Analogue visual scale 0-100

HIV care

Access to HIV services Walking Public transport (Matatu) boda boda Private vehicle

Do you have any concerns about your own health? Yes No

Do you think HIV infection increases the risk of acquiring COVID-19? Yes No

Has your HIV care been affected by any of the following?

Drug stock out No public transport Halt of private vehicles Fear of acquiring HIV at the clinic

Sickness of health care workers Unavailability of HIV services due to the response to COVID-19

Do you think your HIV care will be affected by any of the following?

[figure not shown]
Drug stock out No public transport Halt of private vehicles Fear of acquiring HIV at the clinic

Sickness of health care workers Unavailability of HIV services due to the response to COVID-19

Other medication

Were you prescribed drugs for any of the following?

- Diabetes
- Hypertension
- Anticonvulsants
- Contraceptives
- Anti TB drugs

Are currently taking them?

- Yes No

Are you taking any herb to prevent COVID-19/boost your immunity?

Yes _____ No

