The state of lock-down due to COVID-19 in many parts of the world has led to the halting of services (Roy et al., 2020) and Uganda health service provision has not been spared either. Uganda got first country wide lockdown on 22nd Mar 2020, this lockdown disrupted treatment continuity and globally the supply chains were halted and most patients in chronic care faced challenges (Ebrahim et al., 2020). There is moderate awareness and knowledge of COVID-19 among educated population in India (Roy et al., 2020), but little is documented among youths in rural areas, literature search revealed one documentation on knowledge, attitude and practices of HCW in Makerere University teaching hospital (Olum, Chekwech, Wekha, Nassozzi, & Bongomin). A poor understanding of the disease among youths can result in delayed identification and treatment leading to rapid spread of infections.

[figure not shown]

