3.3 Study population

The study population will comprise of YLWH aged 15 -24 years who are ART naïve or on ART since Jun 2019.

Target population:

Youth living with HIV registered to receive ART at any of the 3 ART clinic in Kiryandongo district :Kiryandongo Hospital, Panyandoli HCIII and Nyakadoti HCII

Accessible population:

[figure not shown]
Youths consented/assented for CFLU, registered for care at Kiryandongo hospital, Panyadoli HCIII or Nyakadoti CII.

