Descriptive analysis will be done for the factors that influence adherence, virological suppression, stigma and retention in care. In addition, the distribution of the independent variables will be done with categorical data summarized using frequencies and percentages. Numerical data will be summarized using means and standard deviations for normally distributed data, and median and inter-quartile range for data that is not normally distributed.

Bivariate Analysis

The relationship between independent variables (age, gender, ART duration, marital status, education status, occupation and religion) and adherence and virological suppression will be analyzed using bivariate analysis made using cross tabular analysis and associations investigated using the Pearson Chi-square test.

The Chi-square test is based on the computational formulae below:

$$\chi^2 = \sum_{i=1}^r \sum_{j=1}^c \frac{(O_{ij} - E_{ij})^2}{E_{ij}}$$

Where

r is the number of categories of the ith explanatory variable

c is the number of categories of the dependent variable

[figure not shown]
O_{ij} is the observed number of observations in the ith explanatory

and jth dependent variable

E_{ij} is the expected number of observations in the ith explanatory?

and jth dependent variable

Further, odds ratios shall be used to analyze the relationship between the dependent variable and the independent variables. Variables found to be significant at p value of p ≤ 0.05 will be considered for the multivariable analysis.

Multivariate Analysis

Multivariable logistic regression will be used to determine the factors that influence adherence or virological suppression and retention in care. Variables found to be statistically significant at $p \leq 0.05$ in bivariate analysis and those considered to have a scientific explanation will be entered into the multivariable model.

The multivariate logistic regression adopted is based on the formulae below:

$$\ln \left[\frac{p_i}{1 - p_i} \right] = \beta_0 + \beta_1 X_1 + \dots + \beta_n X_n$$

[figure not shown]
Where;

X = independent variables

p_i = Probability of being adherent and virally suppressed

$1 - p_i$ = Probability of non-adherence or not suppressed virologically

β_0 = constant ; β_i = coefficient of the determinant

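### In the baseline COVID-19 form, one response option in two questions names HIV where COVID-19 was evidently meant, so answers to that option cannot be interpreted

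*Combined protocol and SAP*

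**What the plan says.** The COVID-19 questionnaire is Appendix xi, headed "COVID-19 KNOWLEDGE ASSESSMENT AMONG YOUTH (BASELINE ONLY" (closing bracket omitted here). Its Section F, on HIV care, has two parallel questions. The first looks back: "Has your HIV care been affected by any of the following". The second looks ahead: "Do you think your HIV care will be affected by any of the following". Each is followed by the same six options. Five are drug stock-outs, lack of public transport, private vehicles being halted, illness among health workers, and HIV services being unavailable because of the COVID-19 response. The sixth, in both lists, is "Fear of acquiring HIV at the clinic".

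Shortly before these lists the form asks "Do you think HIV infection increases the risk of acquiring COVID-19".

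The respondents are defined in section 3.3, where the target population is "Youth living with HIV registered to receive ART at any of the 3 ART clinic" in the district. COVID-19 knowledge is collected at baseline only (section 3.4, Study Objective 2, data collection procedures) and serves specific objective V in section 1.3.2, which is descriptive.

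**The concern.** A person already living with HIV cannot have their HIV care disrupted by fear of acquiring HIV. As printed, the option has no valid affirmative answer for anyone who receives the form. Respondents and interviewers can do one of two things. They can read it literally and leave it blank, or they can assume a slip and answer about COVID-19. The form does not record which they did, so a tick or a blank cannot be given a meaning.

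The practical risk is in reporting. If the option is tabulated beside the other five, a figure near zero could be presented as evidence that fear of the clinic was not a barrier, when the question was never properly put. Section 1.1 makes disruption of care part of the background to the COVID-19 component: "this lockdown disrupted treatment continuity and globally the supply chains were halted and most patients in chronic care faced challenges". A reader would therefore expect Section F to say something usable about why care was interrupted.

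**Working it through.** No figure in the plan depends on this item, so there is nothing to recompute. The check is a reading of the forms side by side.

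**Step 1. Is it a stray extraction error?** The same wording stands in two separate lists, one under the past question and one under the future question. A one-off fault in reading the PDF would be unlikely to produce the same result twice, and nothing is redacted at either place.

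**Step 2. Can the option apply to any respondent?** Section 3.3 and the inclusion criteria under Study Objective 2 restrict the trial to youth living with HIV. No respondent is HIV-negative, so no respondent can acquire HIV at the clinic in the ordinary sense.

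**Step 3. What was meant?** Three features point to COVID-19:
- the form is titled as a COVID-19 assessment;
- a question just above the lists is about the risk of acquiring COVID-19;
- the other options describe pandemic disruption, and one names the COVID-19 response outright.

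This is an inference, but a strong one.

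**Step 4. Is the intended item measured elsewhere?**

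| Place | Nearest content | Fear of COVID-19 as a barrier to care? |
|---|---|---|
| Appendix xi, Section F, earlier items | Whether HIV raises COVID-19 risk; any concern about own health | No: perceived susceptibility and a non-specific worry |
| Appendix xi, Sections B to E | Symptoms, protection, other knowledge, myths | No |
| Appendix viii, Section F | Nine reasons for missing ARVs, such as running out of drugs or being away from home | No |
| Stigma, HIV/TB knowledge and sexual behaviour forms | Other topics | No |
| Focus group guide | General barriers to adherence and clinic attendance | No specific question |

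**Step 5. How much is affected?** Two questions with six options each give 2 × 6 = 12 response options. The faulty wording occupies 2 of them, one per question. The remaining 12 − 2 = 10 are clear.

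**Step 6. How many respondents?** The planned sample is 206. Section A of the form stops the interview for anyone who has never heard of COVID-19, so 206 is an upper bound on those who reach Section F. The documents give no figure for how many will stop.

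**The case against.** The strongest case on the other side is that this is a proofreading slip in a minor form. Much of that stands. The stated COVID-19 objective concerns knowledge, and fear of the clinic is neither a knowledge item nor a listed outcome. Trained research assistants administer the questionnaires and may notice the slip, although the documents do not show that they will, or that all would handle it alike. A literal reader could also stretch the option to HIV re-infection, which the HIV knowledge form mentions in its condom items. That context is sexual, however, and does not fit a fear attached to attending the clinic.

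Several stronger readings are tempting, and the documents do not support them.

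- *That Section F as a whole cannot be interpreted.* Only this option is affected.
- *That Section F is the sole record of interrupted care.* Appendix viii asks how often ARVs were missed and why, with follow-up wording, and asks about health facility visits in the past three months. The missed-visit procedure in section 3.4 also calls for the reason to be documented where known. These sources do not replace the baseline item, but follow-up is not blind to such reasons.
- *That a planned analysis loses a factor.* The univariate section says "Descriptive analysis will be done for the factors that influence adherence, virological suppression, stigma and retention in care", but it does not name the Section F items. The independent variables listed for the bivariate step are age, gender, ART duration, marital status, education, occupation and religion.
- *That a particular number of youth will have their reason unrecorded.* The documents give no rate for fear of COVID-19. An assumed 10% to 40% of 206 would be 206 × 0.10 ≈ 21 to 206 × 0.40 ≈ 82, but that only restates the assumption against an upper-bound denominator. The items also ask whether care was or will be affected, which is not the same as staying away.
- *That the absence of a none-of-these box is part of the fault.* Tick boxes have been lost from this part of the extracted text, and an omitted figure sits beside the second list, so the printed response format cannot be confirmed.

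**Conclusion.** The point holds in a narrow form. One response option, printed in both care-disruption questions of a baseline-only form, cannot apply to the people who answer it. Its answers are uninterpretable, and the fear it was evidently meant to capture is not asked about as a barrier to care on any other reproduced form. Because the form is not repeated, the baseline measure will not be obtained from a later administration.

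The size is small: 2 of 12 response options, for at most 206 respondents, on a descriptive component. The randomised comparison, viral suppression, adherence, retention and the sample size are untouched. The conclusion that the option does not work as printed rests only on the population definition. The conclusion that COVID-19 was meant is an inference from context, which the investigators can confirm. The correction is worth making because it costs almost nothing and prevents a misleading tabulation.

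**What to change.** Confirm the intended meaning, then replace HIV with COVID-19 in this option in both Section F questions, on the paper form and in REDCap, keeping the two in step. The cost is one word in two items, plus whatever notification the ethics committee requires for a form change.

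The protocol version is dated January 2022 and its work plan lists baseline data collection and later recruitment from new sites, so some forms may already be complete. For those, record which wording was used, report this option as not analysable, and do not pool it with answers from corrected forms. The other five options can be pooled across both versions.

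A none-of-these box on each list would help to separate an unaffected respondent from an unanswered question. It is optional and not needed to correct this error.
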